All subjects in the Core Study who discontinue study drug before reaching 12 months of treatment will also be asked to return to the clinic for a 12-month clinical assessment and then again at 24 months. Subjects who discontinue treatment between 12 and 24 months of treatment will be asked to return to the clinic for a 24-month clinical assessment. Subjects who discontinue early from study drug are considered “on study” as long as they continue to return for their regularly scheduled clinical assessments at 12 and 24 months as outlined above, at which efficacy and quality of life will be assessed along with concomitant medications. New AEs will be collected for 4 weeks post last dose and followed up for 12 weeks, or until resolution, whichever comes first. AEs relating to study procedures will be collected until the end of study participation. (revised per Amendment 06) However, subjects who discontinue study drug early are not considered to have ‘completed’ the study as a final Subject Disposition.

The primary reason for discontinuation and all other reason(s) contributing to the subject’s discontinuation from study drug(s) should be collected on the ED from study drug eCRF page. In addition, the date of last dose of study drug(s) will be recorded on the Study Drug Dosing eCRF page. If a subject discontinues study treatment and the study at the same time, the end-of-study procedures (Final Visit) will be followed (see [Section 9.5.5](#)).

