- a: A window of ±3 days will be permitted for Visits 3 and 4. A window of ±7 days will be permitted for Visits 5 and 6. A window of ±10 days will be permitted for Visits 7 to 13 inclusive (including for subjects who discontinue study drug early but who return for clinical assessments at 12 and 24 months). These windows should be calculated from Day 1. A window of ±3 days calculated from the last dose will be permitted for the Follow-up Visits. If use is made of the permitted visit windows, every effort should be made to bring the subject back in line with the “weeks elapsed since 1st dose” at subsequent visits.
- b: Subjects who discontinue taking study drug prematurely for any reason will undergo an ED Visit within 7 days of their last dose of study drug. In addition, Follow-up Visits will be scheduled 4 and 12 weeks after the last dose of study drug (Visit 14 and Visit 15, respectively). Subjects who discontinue study drug before reaching 12 months of treatment will also be asked to return to the clinic for a 12 month clinical assessment and then again at 24 months. Subjects who discontinue treatment between 12 and 24 months of treatment will be asked to return to the clinic for a 24 month clinical assessment. Subjects who discontinue early from study drug are considered “on study” as long as they continue to return for their clinical assessments at 12 and 24 months as outlined above, at which efficacy (MMSE, CDR, ADAS-cog14) and quality of life (EQ-5D, QOL-AD and Zarit’s Burden Interview) will be assessed along with concomitant medications. New AEs will be collected for 4 weeks post last dose and followed up for 12 weeks, or until resolution, whichever comes first. If >4 weeks post last dose, only AEs relating to study procedures will be collected. These 12 and 24 month clinical assessment visits do not need to be attended if they fall within 8 days (visit window) after the ED Visit or within ±8 days of either of the Follow-up Visits (Visit 14 and Visit 15).

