- c: All subjects, regardless of whether they complete all 24 months of treatment or discontinue study drug prematurely, will complete 2 posttreatment Follow-up Visits; one 4 weeks after the last dose of study drug and a second 12 weeks after the last dose of study drug (Visit 14 and Visit 15 respectively). If clinically indicated, more frequent safety assessments can be made as UNS assessments or visits during the posttreatment Follow-up Period. Subjects who have a Grade 2 or greater lymphocytopenia (less than 800/mm³) during the Follow-up Period (ie., at either Visit 14 or Visit 15) should have ALC measured every 4 weeks until resolution or confirmation of a non drug-related cause of the lymphocytopenia. ALC will be derived from the complete blood count (CBC) with differential representing the normal lymphocytes (with atypical lymphocytes removed and presented as a separate count if they are present) and calculated by the white blood cell count × percentage of lymphocytes. Visit 15 will also act as Baseline for subjects who successfully complete the Core Study and will be enrolled into the open-label Extension Phase. (revised per Amendments 01, 02, and 06)
- d: Unscheduled visits may be conducted at any time that additional assessments, including MRI scans, are clinically indicated in the judgment of the investigator. Note that not all assessments indicated under UNS Visits need be conducted – actual assessments needed will be determined by the investigator and will be based on the specific visit needs.e: Only if clinically significant abnormalities are found at Visit 14 and the investigator considers it necessary to repeat at Visit 15, or if the subject is continuing in the Extension Phase.
- f: Measurements of body temperature and sitting blood pressure and sitting heart rate will be obtained.

Table 5 Schedule of Procedures/Assessments in Study E2609-G000-301 (Revised per Amendments 05 and 06)

Phase Period	Randomization													Follow-Up		UNS Visit ^d
	Treatment												ED ^b	14 ^c	15 ^c	
Visit ^a	2	3	4	5	6	7	8	9	10	11	12	13	ED ^b	14 ^c	15 ^c	
Day	1	15	29	57	85	183	274	365	456	547	638	729		757	813	
Week	1	3	5	9	13	27	40	53	66	79	92	105		109	117	
Weeks elapsed since 1st dose	0	2	4	8	12	26	39	52	65	78	91	104		108	116	
Nominal months elapsed since 1st dose	0		1	2	3	6	9	12	15	18	21	24		25	27	
Procedures/ Assessments																

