9.7.1.1.2 SECONDARY ENDPOINTS

The key secondary endpoints of the study are as follows (revised per Amendment 06):

- Change from baseline in ADCOMS at 24 months in the combined studies
- Change from baseline in amyloid PET SUVR at 24 months for brain amyloid levels in the combined studies
- Change from baseline in amyloid PET SUVR at 24 months for brain amyloid levels in the individual studies

The other secondary endpoints of the study are as follows (revised per Amendment 06):

- Change from baseline in the CDR-SB at 24 months for subjects enriched by baseline PET SUVR, eg, between 1.2 and 1.6, in the combined studies
- Change from baseline in the ADCOMS at 24 months for subjects enriched by baseline PET SUVR, eg, between 1.2 and 1.6, in the combined studies
- The rate of change over time (mean slope) based on CDR-SB score over 24 months in the combined studies
- Time to worsening of CDR scores by 24 months (eg, the worsening of global CDR score is defined as an increase from baseline by at least 0.5 points on the global CDR scale on 2 consecutive scheduled visits at which global CDR is undertaken) in the combined studies
- Time to conversion to dementia by 24 months for subjects who were not clinically staged as dementia at Baseline based on clinical diagnosis in the combined studies (revised per Amendment 01)
- Change from baseline in CDR-SB at 27 months (ie, 24 months of treatment plus 3 months posttreatment follow-up) in the combined studies (revised per Amendment 01)
- Change from baseline in ADAS-cog14, MMSE, and FAQ at 24 months in the combined studies
- Change from baseline in ADAS-cog14 Word List (immediate recall and delayed recall) at 24 months in the combined studies (revised per Amendment 01)

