9.7.1.6.1 PRIMARY EFFICACY ANALYSIS

The primary analysis will be based on an intent to treat philosophy without regard to adherence to treatment. The primary analysis of the change from baseline in CDR-SB at 24 months will be performed to compare elenbecestat 50 mg per day versus placebo using a linear mixed effects model for repeated measures (MMRM) on the FAS. The MMRM model will include fixed effects of treatment group, visit, treatment group by visit interaction, baseline CDR-SB, baseline CDR-SB by visit interaction, and randomization stratification variables (ie, region [7 levels], clinical dementia [yes, no], and concurrent AD medication use at randomization [Visit 2] [yes, no]). *ApoE4* status may be included in the model if appropriate. (revised per Amendments 01, 02, and 06) An unstructured covariance matrix will be employed to model the covariance of within subject effect; if MMRM fails to converge then a covariance structure with fewer parameters from the following list will be employed according to the prespecified order in the list until the MMRM converges. The list of covariance structure will include Heterogeneous Toeplitz, Toeplitz, Heterogeneous Compound Symmetry, and Compound Symmetry. This primary analysis will include all observed post baseline data of the change from baseline in CDR-SB without imputation of missing values. The treatment effect for elenbecestat versus placebo will be compared at 24 months based on MMRM model. The LS means and difference in LS means between elenbecestat treatment group and placebo, and corresponding 95% CI will be presented.

The null hypothesis is that there is no difference in the mean change from baseline in CDR-SB at 24 months between elenbecestat 50 mg per day and placebo. The corresponding alternative hypothesis is that there is a difference in the mean change from baseline in CDR-SB at 24 months between elenbecestat 50 mg per day and placebo.

The primary analysis will be repeated to minimize the impact of change in concomitant AD medications where efficacy data after initiation of new AD medications and increase of current AD medications will be censored.

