Time to worsening of CDR scores by 24 months will be analyzed on the FAS using Cox regression model for treatment effect adjusting for randomization stratification factors. *ApoE4* status may be included in the model if appropriate. (revised per Amendment 06) Time to worsening of a CDR score is defined as time from randomization to worsening of the CDR score (ie, the first worsening in 2 consecutive scheduled visits). For subjects whose CDR scores have not worsened by the end of the Treatment Period of the Core Study, the time to worsening of the CDR score will be censored at the date of last CDR assessment for these subjects.

Time to conversion to dementia for subjects who were not clinically staged as dementia at Baseline based on clinical diagnosis will be analyzed on the FAS using Cox regression model for treatment effect adjusting for randomization stratification factors. *ApoE4* status may be included in the model if appropriate. (revised per Amendment 06) Proportion of subjects with

dementia diagnosis at 24 months will be estimated using Kaplan—Meier method based on time to conversion to dementia based on clinical diagnosis. Time to conversion to dementia for subjects who were not clinically staged as dementia at Baseline based on clinical diagnosis is defined as time from randomization to conversion to dementia based on clinical diagnosis. For subjects without clinical dementia by the end of study, the time to conversion to dementia based on clinical diagnosis will be censored at the date of last dementia diagnosis.

The other continuous secondary efficacy endpoints as defined above will be analyzed using the same MMRM model as the primary efficacy analysis to compare elenbecestat 50 mg per day versus placebo on the FAS, using baseline value corresponding to the response variable in the model.

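### The 12- and 24-month return visits for subjects who stopped study drug omit FAQ and dementia staging, so two secondary endpoints lose follow-up that CDR, MMSE and ADAS-cog14 keep

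*Protocol*

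**What the plan says.** Protocol 9.7.1.6.1 sets the strategy for the primary endpoint: "The primary analysis will be based on an intent to treat philosophy without regard to adherence to treatment". To supply the data, subjects off drug return at months 12 and 24, or at month 24 only if they stopped after month 12. Section 9.3.3 describes these as visits "at which efficacy and quality of life will be assessed along with concomitant medications", and 9.5.5 is similarly general. Neither names an instrument or mentions staging. Note b to Table 5 does name them: visits "at which efficacy (MMSE, CDR, ADAS-cog14) and quality of life (EQ-5D, QOL-AD and" Zarit's interview).

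Among the other secondary endpoints in 9.7.1.1.2 is this single line: "Change from baseline in ADAS-cog14, MMSE, and FAQ at 24 months in the combined studies". The same section lists time to conversion to dementia by 24 months and CDR-SB at 27 months. Section 9.7.1.6.2 then states: "The other continuous secondary efficacy endpoints as defined above will be analyzed using the same MMRM model", on the FAS. Conversion is a Cox model on the FAS, and subjects who have not converted are censored at their last dementia assessment. Table 5 note o and the objective in 8.2 put staging at every 3 months.

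On follow-up timing, note c says: "All subjects, regardless of whether they complete all 24 months of treatment or discontinue study drug prematurely, will complete 2 posttreatment Follow-up Visits". For early stoppers note b says: "Follow-up Visits will be scheduled 4 and 12 weeks after the last dose of study drug (Visit 14 and Visit 15, respectively").

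**The concern.** The return visits exist so that outcomes are known whether or not a subject stayed on drug. If the itemised list governs, that holds for CDR, MMSE and ADAS-cog14 but not for FAQ, although FAQ shares their endpoint line, model and population. It also fails for conversion to dementia, where stopping drug ends scheduled staging about 12 weeks later.

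Stopping drug is plausibly related to decline or to side effects, so the resulting missing FAQ values and early censoring may be informative and may differ between arms. A statistical analysis plan cannot recover an assessment that was never made.

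The 27-month endpoint raises a related, smaller issue. Visit 15 is timed from the last dose, so for an early stopper it does not fall at month 27, and no other visit does.

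**Working it through.** **Step 1: what is scheduled.** From the rows of Table 5 and the list in note b:

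| Assessment | Visits 9 and 13 | ED | Visit 14 | Visit 15 | Off-drug 12/24-month visits (note b) |
|---|---|---|---|---|---|
| CDR | yes | yes | yes | yes | listed |
| MMSE | yes | yes | yes | yes | listed |
| ADAS-cog14 | yes | yes | yes | yes | listed |
| FAQ | yes | yes | yes | yes | not listed |
| Disease staging | yes | yes | no | yes | not listed |
| NPI-10 | yes | yes | no | yes | not listed |

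The parenthesis in note b carries no 'eg' or similar, so it reads as a closed list. Section 9.5.1.3.1 describes FAQ among the efficacy assessments, so note b and the general wording of 9.3.3 and 9.5.5 do not agree.

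**Step 2: the plan's own day count.** Visit 15 day = last-dose day + 84 (12 weeks). For a completer: 729 + 84 = 813, which is the Day 813 (nominal month 27) printed in Table 5.

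**Step 3: the same rule for early stoppers.** Gap to month 24 = 729 − Visit 15 day, divided by 30.4375 for months. Shortfall to month 27 = 813 − Visit 15 day.

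| Last dose | Visit 15 | Unstaged to Day 729 | Short of Day 813 |
|---|---|---|---|
| Month 6 (Day 183) | Day 267 | 462 days = 15.2 months | 546 days |
| Month 12 (Day 365) | Day 449 | 280 days = 9.2 months | 364 days |
| Month 18 (Day 547) | Day 631 | 98 days = 3.2 months | 182 days |
| Month 21 (Day 638) | Day 722 | 7 days = 0.2 months | 91 days |

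In the last row Visit 15 is within 8 days of month 24. Note b then waives the return visit, and FAQ and staging are captured at Visit 15. The loss therefore concerns stoppers whose ED or follow-up visits do not coincide with month 12 or 24.

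**Step 4: how many subjects.** The protocol does not give the share that stops drug. Section 9.7.2 gives a 30% dropout rate. Its use can be checked: difference 0.25 × 1.46 = 0.365; SD 2.05; two-sided alpha 0.05; power 90%. This gives 663 per arm (664 by t test), and 663 / 0.70 = 948 per arm, or 1896 in total against the stated 1900. The 30% is thus treated as contributing no 24-month value, which is not the same as stopping drug and returning.

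The share of randomized subjects with a month-24 CDR but no month-24 FAQ is roughly s × r, where s is the share stopping drug and r the share of those who return. Purely as an illustration, s from 20% to 40% and r from 25% to 75% give 0.20 × 0.25 = 5% to 0.40 × 0.75 = 30%. Neither input comes from the protocol.

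**The case against.** The strongest reply is that this is incomplete wording rather than a decision to drop data. Sections 9.3.3 and 9.5.5 promise efficacy assessment without a list, FAQ is an efficacy assessment, and note a places the return visits within the windows for Visits 7 to 13. The Visit 9 and 13 columns mark FAQ, staging and NPI-10. This stands in part: the passages are inconsistent, and some sites may collect everything. But note b is the only itemised instruction, and a site that follows it will not.

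The reply is also right about importance. CDR, MMSE and ADAS-cog14 supply the primary endpoint and every ADCOMS item. FAQ, conversion and 27-month CDR-SB lie outside the sequential testing, and NPI-10 is exploratory. The statement about adherence is made for the primary analysis.

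Three stronger readings are tempting and are not supported:

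- A reader might infer that FAQ is collected only on drug. Table 5 marks FAQ at ED, Visit 14 and Visit 15, and staging at ED and Visit 15, so about 12 weeks off drug are covered.
- A reader might infer that a stopper's Visit 15 score enters the model as month 27 and flatters the arm with more discontinuation. No section makes that assignment. Section 9.7.1.1.2 glosses month 27 as 24 months of treatment plus 3 of follow-up, which an early stopper cannot meet. A bias figure would need that mapping and an invented imbalance between arms; reversing the imbalance reverses its sign.
- A reader might turn the 30% dropout rate into a count of lost FAQ values or staging time. That rate is not described as drug discontinuation, and the return rate is not given.

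**Conclusion.** The point holds as a gap in data collection and an inconsistency within the protocol. As note b is written, off-drug FAQ at months 12 and 24 is not collected, except where another visit coincides. Staging ends about 12 weeks after the last dose. The unstaged time up to month 24 is about 15 months after stopping at month 6, about 9 after month 12 and about 3 after month 18. These figures need only the Table 5 day counts and the assumption that sites follow note b. FAQ and time to conversion therefore lose follow-up that the other scales keep, and censoring of conversion is tied to stopping drug. The direction and size of any bias cannot be derived from the protocol.

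For the 27-month CDR-SB the supported statement is narrower: early stoppers have no scheduled month-27 value. The FAS analysis therefore fills that point for them through the missing-at-random assumption.

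This is a cheap and worthwhile improvement to other secondary endpoints, not a threat to the primary result. The Study 302 schedule is not in the text available, so whether it has the same gap should be checked, since these endpoints are pooled.

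**What to change.** In Table 5 note b, add FAQ and disease staging to the 12- and 24-month return visits, and NPI-10 for its exploratory endpoint. Refer to the same list from 9.3.3, 9.5.5 and the synopsis. If the omission is deliberate, say so and state what FAQ at 24 months and time to conversion are meant to estimate in subjects who stopped drug.

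In 9.7.1.6.2, state that CDRs from follow-up visits are assigned by time since randomization rather than by visit number, and that month-27 CDR-SB is missing for early stoppers.

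The cost is a study-partner questionnaire, which note n already allows by telephone at the investigator's discretion, plus the NPI-10. Staging is more than a reuse of the CDR: it needs a clinician's decision with the existing central review, and adjudication where they disagree. All of it takes place at a visit already held.

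One limit remains. Stoppers would be staged only at months 12 and 24 once Visit 15 has passed, so their conversions would be dated less precisely than under 3-monthly staging.

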9.5.2.2 Description of Procedures/Assessments Schedule

Please refer to [Table 4](#) and [Table 5](#) for the timings of the procedures and assessments to be performed during the study. Screening assessments will be organized into 5 tiers (see [Table 4](#)). See [Section 9.5.1](#) for a full description of the procedures and assessments to be performed during this study.

[Table 6](#) presents the number of blood and CSF samples, and the estimated total volume of blood and CSF that will be collected throughout the study. (revised per Amendment 03) Additional samples may be taken at the discretion of the investigator if the results of any tests fall outside reference ranges or if clinical symptoms necessitate testing to ensure subject safety. Actual specimen volumes may vary based on local regulations. (revised per Amendment 03)

Table 6 Summary of Estimated Blood and CSF Sample Volumes

Assessment	Total Number of Collection Time Points	Sample Volume, Number of Time Points × Volume per Collection (mL)			Total Volume ^a (mL)
		Screening Visits	Visit 2 Baseline (predose) (revised per Amendment 04)	Treatment and Follow-Up Periods	
Blood					
Clinical chemistry (revised per Amendments 03 and 04)	15	1×2.5 mL	1×2.5 mL	13×2.5 mL	37.5 mL
Serum pregnancy test at Screening (females of child-bearing potential only)	0	can use blood drawn for clinical chemistry	can use blood drawn for clinical chemistry	none	no additional volume
Hematology (revised per Amendment 04)	15	1×2 mL	1×2 mL	13×2 mL	30 mL
Coagulation (revised per Amendments 03 and 04)	15	1×1.8 mL	1×1.8 mL	13×1.8 mL	27 mL
Thyroid function tests (thyroid stimulating hormone, free triiodothyronine and free thyroxine)	1	1×5 mL	none	none	5 mL
Viral screen at Screening (Hepatitis B and C) (revised per Amendment 03)	1	1×2.5 mL	none	none	2.5 mL
Viral characterization at Visit 2 (previous exposure to CMV, HSV1, HSV2, etc.) (revised per Amendments 03 and 04)	1	None	1×3.5 mL	none	3.5 mL

Table 6 Summary of Estimated Blood and CSF Sample Volumes

Assessment	Total Number of Collection Time Points	Sample Volume, Number of Time Points × Volume per Collection (mL)			Total Volume ^a (mL)
		Screening Visits	Visit 2 Baseline (predose) (revised per Amendment 04)	Treatment and Follow-Up Periods	
Vitamin B12 at Screening and MMA where available (revised per Amendments 03, 04, and 06)	0	can use blood drawn for TFT	none	none	no additional volume
Blood for immunologic assessments Amendments 01, 04, and 06 ^b	8	none	1×10 mL	7×10 mL	80 mL
Blood for PBMCs (revised per Amendment 06)	4	none	1×10 mL	3×10 mL	40 mL
Blood for immune status (revised per Amendment 04)	8	none	1×5 mL	7×5 mL	40 mL
AD diagnostics and exploratory biomarker (revised per Amendment 04)	1	1×6 mL	none	none	6 mL
PD and exploratory biomarker sample (revised per Amendments 02, 03 and 04)	10	none	1×12 mL	9×6 mL	66 mL
PK analysis (revised per Amendments 02 and 03)	7	none	none	14×2 mL	28 mL
Pharmacogenomic sample (revised per Amendment 03)	1	1×6 mL	none	none	6 mL
All blood samples, total volume collected (revised per Amendments 02, 03, 04, and 06)		25.8 mL	46.8 mL	298.9mL	371.5 mL
CSF					
Amyloid eligibility	1	1×12 mL	none	none	12 mL
PD / PK (optional longitudinal substudy)	1	none	none	1×12 mL	12 mL

Note: Actual volumes may be less, based on regional differences in Central Laboratories.

AD = Alzheimer's disease, CMV = cytomegalovirus, CSF = cerebrospinal fluid, HSV1 = herpes simplex virus 1 (orolabial herpes), HSV2 = herpes simplex virus 2 (genital herpes), PBMCs = peripheral blood mononuclear cells, PD = pharmacodynamics, PK = pharmacokinetic, TFT = thyroid function Test.

a: The total volume includes all blood/CSF collection from Screening through Week 117 (Follow-up Visit); actual volume may vary based on local regulations. (revised per Amendment 03)

b: Immunological assessment samples not required for subjects randomized after 07 Sep 2018 - reducing total blood volume to 291.5 mL (revised per Amendment 06)

